14. VIRTUAL MAILING PROCEDURES

Session /Mailing Procedures:

Baseline

- If participant completes the full package in-person, they will receive a \$50 gift card before they leave the clinic.
 - Each interventionist is responsible for taking care of their own gift cards and welcome package (T-shirt, copy of consent, SOBER handout [BSM group only], and business card).

Instructions:

- Log gift cards out of the safe.
- Complete the GC sheet and make copy of gift card for study records.
 - Ppt. will need to sign off on the sheet. Once completed place in GC binder.
- Present GC to ppt
- Welcome ppt. to the study and hand them their welcome bag.
- Schedule next session (based on their appt. with clinic).

- If the participant takes the packet home, they will need to return the package back or call to complete the assessment over the phone. Once completed, we will mail them a \$50 gift card; if they come back into the clinic, we will give them a gift card in person.
 - Each interventionist is responsible for taking care of their own gift cards and welcome package (T-shirt, copy of consent, SOBER handout [BSM group only], and business card).

Instructions:

- Schedule a time to complete baseline.
 - Inform the ppt. that we will not be able to mail GC without completing the pack first.
- Welcome ppt. to the study and hand them their welcome bag.
 - T-shirt, copy of consent, SOBER handout [BSM group only], and contact card.
 - No GC will be given until pack is completed.

Once baseline is completed:

- Log gift cards out of the safe.
- Complete the GC sheet and make copy of gift card for study records.
 - Once completed place sheet in GC binder (ppt. will not need to sign).
- Mail GC to ppt.

- Mail can be dropped off at the UCH lobby or nearest postal office.
- Use SMART mailer and envelop.

Sessions 1-3 (Virtual)

- After the participant completes all the assessments and the intervention, they will receive their GC. Appointments will be scheduled within 30 day windows.

- **CM Group Instructions:**

- Complete assessments
- Inform ppt. of the GC amount they will receive, and to please allow 2-3 business days to arrive.
 - \$50 for completing assessments.
 - Additional GC will depend on the following:

Urine toxicology results

- If participant is compliant, buprenorphine in their urine, we will spin the virtual wheel for them and inform them of the amount received.
- If participant is not compliant, no buprenorphine in their urine, we will inform them that they will not be able to participate in the number wheel at this time.

- Study team will take a screenshot of the number wheel and will text or email ppt. the results; only when applicable.

- Place ppt. ID and GC amounts in the GC google sheet for future mailing.
 - Study staff that is present in the clinic will be responsible for GC mailings for that day.
 - If no staff is available that day, please inform the ppt. that they will receive GC in X number of days (based on when staff will be in clinic next).
- Mail GC to ppt.
 - Mail can be dropped off at the UCH lobby or nearest postal office.
 - Use SMART mailer and envelop.

- **BSM Group Instructions:**

- Complete assessments and intervention.
- Inform ppt. of the GC amount they will receive (\$50), and to please allow 2-3 business days to arrive.
- Place ppt. ID and GC amounts in the GC google sheet for future mailing.

- Study staff that is present in the clinic will be responsible for GC mailings for that day.
- If no staff is available that day, please inform the ppt. that they will receive GC in X number of days (based on when staff will be in clinic next).
- Mail GC to ppt.
 - Mail can be dropped off at the UCH lobby or nearest postal office.
 - Use SMART mailer and envelop.

Note: If study team does not have access to postage stamps, Wednesdays and Fridays will be designed gift card mailing days. Study team will alternate days that they deliver gift cards to the UTHSC main campus.

- Wednesdays: Red bag will be dropped off at the Pauline bldg.
- Fridays: Study team will take the red bag to the mail room in the Madison bldg.

Instructions:

- Use the GC google sheet to confirm gift cards that need to be mailed.
- Log gift cards out of the safe.
- Complete the GC sheet and make copy of gift card for study records.
- Once completed place sheet in GC binder (ppt. will not need to sign).
- Place GC in red bag and take to designed mailing area for that day.
 - Use SMART mailer and envelop.
- Log mileage from clinic to the main office and submit monthly.

Session 4 (Virtual): Part 1

- After the participant completes Part 1 of the assessments and the intervention, they will schedule Part 2 of the session .

Instructions:

- Complete Part 1 assessments
- Complete the intervention
- Schedule follow-up call with the RA.
 - RA will be responsible for logging ppt. ID, completion date, and GC amount in the google sheet and notifying team of completion status.
 - Note: Ppt. will not receive GC unless they complete all parts of the session (Part 1 & 2 Assessments and intervention).

Session 4 (Virtual): Part 2

To be completed by RA.

- Complete Part 2 assessments and log session info. in the google sheet for future GC mailing.

Instructions:

- **Complete Part 2 assessments**
- **Complete treatment satisfaction survey**
- **Notify team of completion (via email or GroupMe msg.).**
- **Log study ID, date of completion, and GC amount in the google sheet**
- **Mailing will be the same as Sessions 1-3.**

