8.6. Intervention Sessions

Prior to the session, Interventionists will prepare for the brief assessment conducted during each treatment session by finding the participant in the Filemaker database, or if offline, entering the participant information on the top of the assessment materials.

Interventionists will also prepare to administer the appropriate session (1, 2, 3, or 4) (within the appropriate condition).

In addition, Interventionists will prepare the recording device to ensure that the session is recorded. If remote, the interventionist will text or email the participant a Zoom telephone number with a meeting ID for them to call and be placed in a meeting. The interventionist will ensure that Zoom is recording once permission is granted from participant. All sessions will be recorded and uploaded to OneDrive folder (SMART Project 3/Recordings) and labeled with the participant's study ID, session number (1, 2, 3, 4), condition (CM vs. BSM), and staff initials. (e.g. 301 S2 BSM AB)

At each session , the Interventionist will meet with the participant to complete the assessment questionnaires and complete the intervention – either a BSM session or a wheel spin for additional gift cards for CM (if requirements are met).

If the participant drops out of treatment at the Center for Addiction Science, they will no longer receive the CM or BSM. However, all assessments will be conducted regardless of the participant's adherence to medical treatment at the CAS. Upon completion of the assessment, participants will still earn the \$50 gift card. This will allow us to understand the reason for the participant's non-adherence to treatment, and to evaluate whether these individuals pursue treatment elsewhere.

The intervention scripts are available in section 13 of the manual of procedures.

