8.10. Option for Scheduling

Since the patient will have scheduled their next physician appointment, we will not schedule their next research appointment (unless we are remote, in which case the session will be yoked to their CAS appointment, to be scheduled immediately following their appointment at the CAS). We will use the medical charts to block off time for the participant's S1 (ex: the participant schedules a 2:00 pm doctor's appointment, their research appointment will be at 2:45 pm). Appointment times are not stringent, so if a participant gets done with their physician visit early and their assigned counselor is free, they can complete their session early.

Note on Assessment for participants who fail to attend treatment:

The study staff will continue to contact the participant to complete their assessments if a participant stops attending CAS. Study staff will inform the participant that they will not be receiving treatment (i.e., CM or BSM intervention). However, they can continue to earn gift cards for completing assessments. Assessments and intervention may occur in two visits if a participant missed their clinic visit, but later rescheduled and completed their clinic visit **before the closing of the session window.** Study staff will also inform the participant that information shared will not be disclosed to clinic staff or doctors.

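### The virtual Session 4 gift-card rule requires the intervention, which clinic dropouts do not receive, although other sections promise them payment for assessments alone

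*Protocol*

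**What the plan says.** **The restrictive text (Protocol Section 14).** Under Session 4 (Virtual): Part 1, the card rule is: "Ppt. will not receive GC unless they complete all parts of the session (Part 1 & 2 Assessments and intervention". The sequence is also set there: "After the participant completes Part 1 of the assessments and the intervention, they will schedule Part 2 of the session". Neither sentence mentions participants who no longer receive the intervention.

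For virtual Sessions 1-3 the lead sentence is softer: "After the participant completes all the assessments and the intervention, they will receive their GC". The BSM list there begins with "Complete assessments and intervention" before the card is announced, while the CM list gives the dollar amount as "50 for completing assessments".

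**The text on dropouts.** Section 8.6 (Intervention Sessions) says: "If the participant drops out of treatment at the Center for Addiction Science, they will no longer receive the CM or BSM". It then keeps all assessments in place and continues: "Upon completion of the assessment, participants will still earn the" 50-dollar card. Section 8.10 (Option for Scheduling) has staff tell people who stop attending that they will get neither intervention, and adds: "However, they can continue to earn gift cards for completing assessments". Section 8.2.1 (Consent) has participants informed that assessments are offered and paid whatever their adherence to visits or medication. Section 8.8.2 (Gift Card Distribution) ties the 50-dollar card to the assessment and not to the intervention. The Participant Withdrawal section (numbered 18.13.3) says inactive participants still get the 50-dollar card on completing a session, and it lists S4 by name.

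**The concern.** The two sets of instructions cannot both be followed for a dropout who completes the Session 4 assessments. Section 14 is the step-by-step text used by the research assistant who logs the Session 4 card, so a literal reading could be applied in practice.

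What is at stake is Part 2, the blinded call. Table 1 (Section 12.1) shows treatment satisfaction only in the 8-week blind column. Delay discounting, engagement in substance-free activities and EQ-5D-5L appear only at baseline and in that column. None of these four post-baseline values can be recovered from the chart or from Sessions 1-3. Satisfaction is a primary outcome in Section 3.3, and delay discounting is part of an SAP hypothesis.

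Removing the incentive from people who left treatment could make these data missing in a way related to the outcome. Satisfaction would then come mainly from retained participants, and would look too favourable if dropouts are less satisfied. Withholding the card would also break the payment statement made at consent.

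**Working it through.** The plan has no figure to reproduce on this point. The check is a comparison of texts, followed by a small sensitivity calculation.

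**Step 1. The two rules for one person.** Take a participant who has left the clinic and completes the Part 1 and Part 2 assessments of a virtual Session 4.

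| Source | Condition for the card | Result for this person |
|---|---|---|
| Section 14, Session 4 | Part 1 and Part 2 and intervention | 0 dollars |
| Sections 8.6 and 8.10 | Assessment completed; no CM or BSM given | 50 dollars |
| Section 8.2.1 | Paid for assessments whatever the adherence | Paid (amount not stated there) |
| Section 8.8.2 | Assessment completed | 50 dollars |

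The intervention term is always false for a dropout, so the Section 14 condition can never be met. No section exempts dropouts from it.

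**Step 2. Scheduling.** Section 14 lists the Part 1 assessments, then the intervention, then the booking of Part 2. Read literally, a person who skips the middle step has no route to Part 2. By contrast, Section 3.4.3 expects all participants to complete the blinded assessment, Section 3.6.3 lists the call without an intervention condition, and item 15 of the satisfaction form (Section 12.2.21) is addressed only to those who dropped out.

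**Step 3. By arm.** In BSM the intervention is a counselling session, and a dropout clearly does not complete it. In CM, a participant without buprenorphine in urine gets no spin and is simply told so (Section 8.5.1). What completing the intervention means without a spin is therefore undefined, and the conflict is less sharp.

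**Step 4. Sensitivity per missing person.** Inputs: 20 participants per arm (Section 3.5). The number missing, k, and the completer-minus-dropout gap, g, are not given and are left as symbols.

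- Share of an arm lost per missing Part 2: 1/20 = 0.05, or 5%.
- Full-arm mean = [(20 − k) × completer mean + k × dropout mean]/20. The observed mean is the completer mean, so the shift is (k/20) × g. For k = 1 and g = 1 point, this is 0.05 points.
- Worst-case range for an arm mean on a 1-10 item such as satisfaction item 16 (an example only, since no satisfaction score is named): (10 − 1)/20 = 0.45 points wider per missing person.

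These figures hold for any missed Part 2 call. They show what one loss costs, not how many losses the card rule would cause.

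**The case against.** The strongest reply is that the Session 4 sentence was never aimed at dropouts. It sits in a mailing procedure, directly after the steps for people receiving the session. Its natural purpose is to hold the card until Part 2 is done, much as the baseline card is held until the assessment pack is complete. On that reading it encourages Part 2 completion. Sections 8.6 and 8.10 address dropouts directly, and Section 10 says gift-card procedures carry over with slight changes, naming only mailing and a tracking sheet.

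This is a likely intent, but the sentence does not say so. The withdrawal section comes closest to resolving the matter, yet its condition that the session be completed leaves the same question open for someone who completes only the assessments.

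The protective text does reduce the risk. Section 8.5 tells staff to keep trying to assess after the S4 window, Section 8.13.1 puts assessments first when intervention sessions cannot be done, and the withdrawal section prompts staff to ask for the last follow-up. Some dropouts would also be hard to reach under any payment rule.

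A reader might infer that someone leaving before Session 1 loses every post-baseline assessment card. The documents do not support that. The Sessions 1-3 sentence says when the card comes, not that it comes only then, and the CM list pays for assessments alone. The Session 4 sentence is the only express prohibition.

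**Conclusion.** The inconsistency is real and should be corrected. It covers virtual Session 4 only, is clearest in BSM, and concerns one 50-dollar assessment card per affected participant. The conclusion rests on a literal reading of Section 14, which the documents neither confirm nor limit.

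The consequence is a risk and not a demonstrated loss. No dropout rate is given, and the share of missing Part 2 data due to this rule could lie anywhere from none to all. Upward bias in satisfaction requires that dropouts are less satisfied, and the direction of any CM-BSM bias is unknown.

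Two stronger inferences are not supported. A reader might think the adherence comparison is compromised, but attendance and urine results come from the chart (Sections 3.4.4 and 3.6.4) whether or not a card is paid. A reader might also think the SAP hypothesis on time allocated to substance-free activities is lost. However, the engagement form collected at Part 2 (Section 12.2.16) rates helpfulness, not time, and Table 1 schedules the time worksheet at baseline only.

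**What to change.** In Section 14, Session 4 (Virtual):

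- Keep the present order (Part 1 assessments, intervention, Part 2) for participants who receive the Session 4 intervention, so that they do not rate satisfaction before it is delivered.
- Add that, for participants who do not receive it, Part 2 is scheduled once the Part 1 assessments are done.
- State that the 50-dollar Session 4 assessment card depends on the Part 1 and Part 2 assessments only. This also removes the need to define completion of CM without a spin for payment purposes.
- Align the Sessions 1-3 lead sentence and the BSM list with Sections 8.2.1, 8.6, 8.8.2 and 8.10.

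Who receives CM or BSM and the CM wheel reward stay as they are. The payments are already promised elsewhere in the protocol, so no new incentive is created. The cost is a text edit and IRB notification.

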Appendix B. Withdrawal Letter

DATE:

Dear Study Participant:

This is to notify you that as you requested, you have officially withdrawn from the study "*Testing the Effects of Contingency Management and Behavioral Economics on Buprenorphine-Naloxone Treatment Adherence Using a Sequential Multiple Assignment Randomized Trial*" (SMART) Design Internal Review Board Number: 20-07418-XP UM. Please be aware that all data you have provided for this study has been destroyed and is not accessible by anyone.

Please contact the study team if you should have any questions regarding your participation in this study in the future.

Sincerely,

[name], CCRP

Senior Research Project Coordinator
Center for Population Sciences
Department of Preventive Medicine
University of Tennessee Health Science Center
[name]
[name]
[contact]

Statistical Analysis Plan: SMART Project 3 (Efficacy Study)

Because these analyses will focus on determining and intervention feasibility and satisfaction, and preliminary intervention effect sizes (with less concern focused on testing for statistical significance), outcome analyses will be conducted using a separate analysis for each outcome at each follow up observation. To compare groups, baseline and follow up variables will be entered into a 5 (baseline vs. follow ups at 1, 2, 3, and 4 weeks) by 2 (CM vs. BSM) analysis of variance (ANOVA) which will yield effect sizes for time, and interactions of time by intervention. The primary dependent variables will be attendance at physician visits, saliva drug screen data (positive for buprenorphine and negative for illicit opioids), and prescription drug monitoring. We hypothesize that a greater number of CM participants will demonstrate adherence to buprenorphine-naloxone than BSM, but that those randomized to BSM will report increased time allocated to substance-free activities, decreased delayed reward discounting, and demand for opioid.

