3.3. Design and Outcomes

This project will use a randomized design to compare treatment satisfaction and effectiveness of Contingency Management (CM) and Brief Motivational Intervention + Substance Free Activities Session + Mindfulness-Based Adherence Promotion (BSM) for medication adherence in patients who are initiating buprenorphine-naloxone treatment at our Center for Addiction Science (N=40). The interventions will take place across the first 4 physician visits of buprenorphine-naloxone treatment, starting after treatment intake.

Primary outcomes will include feasibility and satisfaction at the fourth weekly intervention visit, and an efficacy comparison of intervention group differences in buprenorphine-naloxone treatment adherence, defined as (1) attendance at physician visit AND (2) buprenorphine-naloxone presence in urine toxicology.

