3.5.2. Inclusion/Exclusion

Participants must be 18 years of age or older and presenting for buprenorphine-naloxone treatment. Patients must be eligible to receive buprenorphine-naloxone medication (e.g., Suboxone, Bunavail, Zubsolv) during their visit at CAS. This study is open to all eligible participants.

Notably, due to the nature of medical treatment, approximately 5% of new patients will not follow the "regular" intake course of buprenorphine due to previous treatment and/or treatment initiation using injectable depot buprenorphine administration (which requires fewer physician visits). Because all patients initiating treatment are at risk for drop out/low adherence, we wish to enroll these participants if at all possible under the stringent timelines for this study. We will therefore enroll unusual buprenorphine-

naloxone initiation timelines on a case by case basis, dependent upon the ability to complete study procedures within the study timeline.

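### The SAP analyses the drug screen apart from attendance with no rule for a screen not done, so the CM-BSM screen comparison is conditioned on post-randomization attendance; the protocol's composite avoids this but is not listed

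*SAP*

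**What the plan says.** The SAP is one paragraph. For its between-group model, "baseline and follow up variables will be entered into a 5 (baseline vs. follow ups at 1, 2, 3, and 4 weeks") by two-arm ANOVA, and its primary dependent variables are "attendance at physician visits, saliva drug screen data (positive for buprenorphine and negative for illicit opioids), and prescription drug monitoring". The sentence before the model says that "outcome analyses will be conducted using a separate analysis for each outcome at each follow up observation". The paragraph defines no analysis population, no handling of missing values and no score for a screen that was not obtained.

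The protocol (section 3.3) defines adherence as a composite: ("1) attendance at physician visit AND (2) buprenorphine-naloxone presence in urine toxicology". The visit forms in 12.2.7 to 12.2.10 mark a visit adherent only when both items are Yes, so a missed visit is not adherent. The SAP does not list this composite.

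The screen result is taken from the clinic chart (3.6.2), and the Urine Toxicology form in 12.2 records urine collected by the clinic, with Yes and No as the only answers. Participants who leave treatment keep completing questionnaires (8.6 Intervention Sessions; 8.10 Option for Scheduling), but no specimen collected by the study is described. A missed visit can be made up before the session window closes (8.10).

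**The concern.** Attendance happens after randomization, and both interventions aim to change it. Section 3.5.2 explains its broad enrolment this way: "Because all patients initiating treatment are at risk for drop out/low adherence". A screen is missing largely because the participant did not attend, which is itself half of the protocol's definition of non-adherence. Comparing screens among people who have them therefore compares selected subsets of the two arms, and the randomized comparison is lost for that variable.

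What is at stake is an effect size. The SAP's stated product is preliminary effect sizes, and section 3.2 makes efficacy here a step towards Project 4. A screen effect estimated among attenders answers a different question from how many randomized participants were taking buprenorphine at each visit.

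**Working it through.** The documents give no attendance, drop-out, response or power figure, so there is nothing of the plan's own to reproduce beyond 20 + 20 = 40 (section 3.5). All rates below are assumptions.

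**1. What the ANOVA does with a missing cell.** A classical repeated-measures ANOVA needs every level for every participant. Run on test data with one cell removed, the statsmodels routine stopped with an unbalanced-data error. With no other rule, the usual way forward is to drop the participant.

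**2. How many would remain.** Baseline is observed for all. With independent attendance probability *a* at each of four return visits, expected full attenders per arm = 20 × *a*⁴:

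| *a* | *a*⁴ | of 20 |
|---|---|---|
| 0.95 | 0.815 | 16.3 |
| 0.90 | 0.656 | 13.1 |
| 0.80 | 0.410 | 8.2 |
| 0.70 | 0.240 | 4.8 |

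**3. CM acting through attendance only.** Assume permanent drop-out of 5% (CM) and 12% (BSM) per visit, and 95% buprenorphine-positive among attenders in both arms.
- Full attenders: 20 × 0.95⁴ = 16.3 and 20 × 0.88⁴ = 12.0.
- Screen difference among full attenders, or among each visit's attenders: 0.95 − 0.95 = 0.
- Mean attendance, CM: (0.950 + 0.903 + 0.857 + 0.815)/4 = 0.881. BSM: (0.880 + 0.774 + 0.681 + 0.600)/4 = 0.734. Difference 0.147.
- Composite among all randomized: 0.95 × 0.147 = 0.140, about 14 points.

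**4. Without permanent drop-out.** Attendance 0.90 (CM) and 0.75 (BSM), 90% positive among attenders: composite 0.810 against 0.675, a difference of 13.5 points on 20 against 20. Among full attenders the difference is 0, on 20 × 0.90⁴ = 13.1 and 20 × 0.75⁴ = 6.3 expected participants. Across five such scenarios the composite difference was 12 to 18 points; among full attenders it was 0 to −7. The −7 comes from assuming 85% (CM) and 92% (BSM) positive among attenders.

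**5. The two readings of the SAP compared.** This simulation (200,000 per arm) gives each person one propensity (logit-normal, SD 1.5) that drives both attendance and a positive screen. CM is better by one logit on both.

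| Mean attendance, CM / BSM | Full attenders | Each visit's attenders | All randomized, missed = not adherent |
|---|---|---|---|
| 81.0% / 67.2% | 3.2 points | 7.2 points | 17.3 points |
| 74.7% / 58.7% | 3.7 points | 8.6 points | 18.9 points |

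Analysing each follow-up separately reduces the shrinkage but does not remove it.

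**6. Precision after the fix.** For 0.810 against 0.675 at one visit, SE = √(0.81 × 0.19/20 + 0.675 × 0.325/20) = 0.137, so the 95% interval is about ±27 points. Power in the five scenarios was 13% to 24%.

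**The case against.** The case for the plan has real substance.

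- **A reader might infer that the SAP removes drop-outs and compares full attenders only.** It does not say so. It is silent, and full attenders follow only from the repeated-measures reading. The sentence on separate analyses would lose one visit's record, not the person. Make-up visits also recover some screens, and a Yes/No form might store a missing screen as No. What remains is that both readings condition on attendance. Storing an absent specimen as No is no remedy either: the SAP's screen also requires illicit opioids to be negative, so an empty record would count in the participant's favour there.
- **A reader might infer that a CM effect would vanish from the trial.** The documents do not support that. Attendance is itself a primary dependent variable and can be recorded for everyone; in step 3 it differs by 14.7 points. A screen difference of 0 among attenders is also the right answer to a question about attenders. The defect is confined to the screen effect size and what it is taken to mean.
- **A reader might extend the point to the self-report outcomes.** Table 1 (12.1) schedules delay discounting and substance-free activities only at baseline and the blinded 8-week assessment, and time spent on activities only at baseline. A missed assessment at Sessions 1 to 3 cannot remove anyone from those. Of the hypothesised BSM outcomes, only the opioid purchase task is taken at every session, and assessments continue after treatment drop-out.
- **The protocol already holds the remedy.** It does: its composite scores a missed visit as not adherent. The SAP's hypothesis speaks of adherence, but its list of dependent variables splits the composite into parts.
- **This is a pilot with "less concern focused on testing for statistical significance".** That lowers the importance of tests and raises that of an effect size with a clear meaning.

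**Conclusion.** The concern holds for the drug screen. Analysed apart from attendance and without a rule for screens not done, it gives a CM-BSM comparison conditioned on a post-randomization event that the interventions target. If CM works through attendance, the screen effect size is understated: under assumed rates, 0 points against about 14 when effects run through attendance alone, and roughly 3 to 9 points against 17 to 19 when one propensity drives both. These sizes illustrate the mechanism and do not predict this trial. The step 3 model of permanent drop-out is also simpler than the protocol, which allows for dropping out and returning (12.2.11). The attendance and prescription-monitoring variables are not affected in this way, and the self-report outcomes hardly at all. With 20 per arm the corrected estimate will still be imprecise, which suits the SAP's estimation aim.

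**What to change.** Amend the SAP as follows.

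1. Make the protocol composite (attended and buprenorphine present), at each of the four return visits, the primary efficacy variable for all 40 participants as randomized.
2. Count a visit missed and not made up within its window as not adherent, in line with the forms in 12.2.7 to 12.2.10. Those forms ask about the scheduled day and time, so state how a made-up visit is scored. Report separately any attended visit with no recorded result.
3. Replace the ANOVA for this outcome with per-visit risk differences and confidence intervals, or with a GEE or mixed logistic model with a small-sample correction.
4. Report screens among attenders as descriptive or sensitivity results only, and do not count an absent specimen as opioid-negative.
5. Use a mixed model on all available records for self-report measures taken at every session, such as the opioid purchase task.
6. Reconcile "saliva drug screen data (positive for buprenorphine and negative for illicit opioids") in the SAP with the urine screen in protocol section 3.3 and the toxicology form.

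The cost is SAP wording and standard software. The composite is already calculated in the study database, and no new data are needed.
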